Assessments. Assessments will be administered via telephone by a D-H research assistant blind to group assignment. Participants will complete outcome assessments upon enrollment (T1) and at 8 weeks (T2), 20 weeks (T3) and 44 weeks (T4) later. The T2 assessment captures the short-term outcomes of the most intensive part of the intervention (i.e., after six weekly sessions). The T3 assessment will capture the short-term outcomes at the end of the full intervention. The T4 assessment explores the sustained effect of BA/PS (six months after BA/PS ends). Our decision to include the T4 assessment was influenced by a systematic review that indicated it often takes six months to see maximum effects of interventions targeting participation in adults with physical disabilities.[46] The study aim is to test whether the BA/PS intervention affects the “slope” of functional recovery over time. With the longitudinal data, we will also be able to explore the pace of improvement and whether the two groups differ at these clinically relevant time points.

[figure not shown]
4. Subject Selection

Inclusion Criteria with justification

1. Age of 18 years or older.
2. Experiencing reduced participation (i.e., a score of ≥ 10 on the modified Work and Social Adjustment Scale[47]).
3. Females diagnosed with Stage 1-3 breast cancer and within one year of completion of locoregional treatment and/or chemotherapy with curative intent and absence of disease recurrence.

Biological variables of age and gender. In our pilot studies, the intervention has been flexible enough to be used with various challenges that occur across the age range.[25, 29] This proposal’s focus upon female breast cancer survivors reflects our pilot research population and allows us to focus recruitment resources with a smaller, closely aligned number of providers. We have decided to focus on females with breast cancer because of the very low prevalence rate of breast cancer in males. Because the D-H and UAB sites see a mean of 3.8 males each year with breast cancer, we will not enroll enough males to allow us to draw sound conclusions that are generalizable to a male population.

Medical co-morbidities. We considered the advantages and disadvantages of excluding women who have medical co-morbidities that affect their daily activities. Cancer survivors report an average of five

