Minimally important differences. The minimally important differences (MID) between the two study arms are taken to be 10% of the practical range of the outcome variable[31] and thus the MIDs are 3.94, 3.95 and 11.2 for satisfaction with participation, ability to participate, and quality of life, respectively. Note that these MIDs are not data dependent, although standard deviations might change for different data sets. We will assume the standard deviation for the two PROMIS scales are both 10 according to the scoring manual and the standard deviation for FACT-B is 24, as estimated from our third pilot study.[29]

Estimated attrition. To estimate attrition, we examined the attrition seen in our three preliminary studies. One of the preliminary studies was an RCT,[25] two studies used a single arm design,[29] and each of the studies had at least three assessments. On average, 80% of our participants completed all study activities, and thus we expect an attrition of ~20% (if 300 people enroll, at least 240 participants will complete the study).

Power. Using a Time-Averaged Difference approach,[81] at a corrected significance level of $.05/3=.017$, and with three time-points post baseline, the required sample size to test for the minimally important effects of BA/PS on participation (PROMIS scales) ranges from 63 to 117 in each arm to achieve 80% power for within subject correlations ranging from 0.2-0.8. The required sample size to test for the minimally important effect of BA/PS on quality of life (overall FACT-B score) ranges from 45 to 83 in each arm to achieve 80% power for within subject correlations ranging from 0.2-0.8. An FDR correction (see section C.7.3) will be used at the time of analysis which will provide more power than a Bonferroni correction and adequate control to the number of Type I errors.

Statistical Methods

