Modeling. A longitudinal model fitted with linear mixed methods will be used for each outcome. Numerical outcomes with markedly non-normal distributions, if any, will be modeled with more appropriate error distributions than the default normal (e.g., lognormal or generalized beta distributions). The focus of inference will be the between-group difference in outcome trajectories over the study time points, modeled by a time by group interaction. A random effect for subject will be fitted to account for covariance among repeated measures on the same individuals. If necessary, we will conduct covariate adjustment for baseline factors unbalanced between the groups or predictive of dropout. Time will be modeled as a categorical variable, to avoid the strong assumption of linear trajectories, and therefore the single test for the interaction effect will be a multiple-degree of freedom test. Model-predicted outcome means (a.k.a. LS-Means) by group at each time point will be computed to facilitate interpretation. The overall treatment effect will be computed as the between-group difference in change from baseline (change from T1 averaged over T2 to T4) estimated with a linear contrast.

Handling of Missing Data

Mixed modeling techniques and covariate adjustment will reduce the impact of missing data, as the missingness is not assumed completely at random (MCAR) but conditionally (on the covariates) at random (i.e., MAR, a milder assumption).[82] Should dropout exceed the 20% allowed by the sample size (section C.7.5), non-parametric multiple imputation[83] will be employed to determine the robustness of the conclusions for the main analyses under the milder MAR assumption. Because missing data due to non-ignorable or non-random drop out (i.e., MNAR) does not depend on the observed data, it presents the most complex situation to handle. Because of the non-invasive, supportive nature of the BA/PS intervention, as well as the attention control condition, *a priori*, we do not expect to encounter non-random dropout (and therefore MNAR). However, we will examine the tracking system records and logs with regard to dropout, to determine the main reasons for dropout. If sufficient indication of an MNAR mechanism is found, sensitivity analyses under different assumptions for the missing data mechanism will be conducted, following the methodology described by Molenberghs and Kenward[84] in which the missing data mechanism needs to be modeled explicitly.

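### Within-woman covariance rests on a subject random effect alone, so the interval for the averaged change from T1 can be too wide or too narrow; the 3-df interaction test is only mildly affected

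*Combined protocol and SAP*

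**What the plan says.** Section 9, Modeling, sets one linear mixed model per outcome. On covariance it says only this: "A random effect for subject will be fitted to account for covariance among repeated measures on the same individuals". On the mean structure it is careful: "Time will be modeled as a categorical variable, to avoid the strong assumption of linear trajectories". The arms are then compared by one joint test of group by time. With four visits and two arms that test has 3 degrees of freedom, and the section makes it the focus of inference.

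The same section then defines the effect estimate: "The overall treatment effect will be computed as the between-group difference in change from baseline (change from T1 averaged over T2 to T4", obtained from a linear contrast. Section 3 (Assessments) puts follow-up "at 8 weeks (T2), 20 weeks (T3) and 44 weeks (T4) later", and says the longitudinal data will also be used to "explore the pace of improvement and whether the two groups differ at these clinically relevant time points".

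The Power paragraph sizes the trial "with three time-points post baseline, the required sample size to test for the minimally important effects of BA/PS on participation", at "80% power for within subject correlations ranging from 0.2-0.8". No section states a residual covariance structure, a random slope, a robust standard error, a degrees-of-freedom method or a check of the covariance.

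**The concern.** A random intercept with independent residuals forces every visit to have the same variance and every pair of visits the same correlation. Here the gaps between visits are 8, 12 and 24 weeks. T1 precedes all treatment, and women enter on a cut-off for participation restriction (WSAS of at least 10), which could make the T1 spread differ from later spreads. The plan relaxes linearity in the means but leaves an assumption of similar strength in the covariance.

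The averaged contrast sets T1 against the other three visits. Its true variance therefore depends on the T1 variance and on how T1 correlates with follow-up, whereas the model uses one pooled residual variance. If the two differ, the model-based interval for the overall treatment effect has the wrong width. Single-visit changes from baseline, which feed the exploratory look at pace of improvement, are exposed in the same way.

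**Working it through.** **1. The plan's own figure.** Inputs from section 9 (Sample Size Determination): MID 3.94, SD 10 (PROMIS); MID 11.2, SD 24 (FACT-B); alpha .05/3; power 80%; three post-baseline visits; correlation ρ of 0.2 to 0.8. A two-sided time-averaged difference gives

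n per arm = 2(z₁₋α/₂ + z₀.₈)² SD² (1 + 2ρ) / (3 d²).

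- PROMIS: 62.9 and 116.9, so 63 and 117, as stated.
- FACT-B: 44.9 and 83.3, so 45 and 84 (83 with alpha rounded to .017); stated 45 and 83.

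The formula uses one correlation among the post-baseline visits and no T1. The 0.2-0.8 range therefore says nothing about how T1 correlates with follow-up.

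**2. Level under a random intercept (complete data, large sample).** Let S be the true 4×4 covariance, C the centring matrix and c = (-1, 1/3, 1/3, 1/3).

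- Fitted residual variance: s² = trace(CSC)/3. With unit variances this is 1 minus the mean of the six correlations.
- Model variance of the contrast: s²·c′c = (4/3)s². True variance: c′Sc.
- SE ratio r = √(model/true); actual level = 2[1 - Φ(1.96 r)].
- 3-df test: weighted chi-square, weights being the eigenvalues of (s²LL′)⁻¹LSL′, where L takes the three changes from T1.

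*Example A*: T1 correlates .4 with later visits, which correlate .7 with each other. Mean correlation .55, s² = .45, model variance .60. True variance 1 + (1 + 1.4)/3 - 0.8 = 1.00. r = √.60 = .775; level 12.9%.

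*Example B*: T1 .6, later .5. Mean .55, model variance again .60. True variance 1 + (1 + 1)/3 - 1.2 = .467. r = 1.134; level 2.6%.

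*Example C*: correlation .60·exp(-weeks/77), equal SDs. Pairwise correlations .541, .463, .339, .513, .376, .439; mean .445; s² = .555; model variance .740; true .734; r = 1.004; level 4.9%. For T4-T1 alone the model variance is 1.110 against a true 2(1 - .339) = 1.322, giving 7.3%. For T2-T1 the true variance is 2(1 - .541) = .918, giving 3.1%.

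**3. All ten patterns, nominal 5%.** Every pattern is an assumption.

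| Assumed pattern | Averaged contrast, analytic | Same, simulated |
|---|---|---|
| T1 .6, later .5 | 2.6% | 2.7% |
| SDs 8, 9, 10, 10 with decay in weeks (two curves) | 3.2-3.3% | 3.8% |
| Decay in weeks, equal SDs (a = .60 and .84) | 4.8-4.9% | 4.8-4.9% |
| AR(1) by visit order, .6 and .8 | 7.8%, 8.8% | 7.6%, 9.7% |
| T1 .6, .5, .4; later .7 | 8.4%, 11.0%, 12.9% | 7.6%, 10.8%, 12.4% |

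The simulation had 150 per arm, no true effect, random monotone dropout reaching 20% by T4, and 10,000 runs per pattern.

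- 3-df test over these patterns: 5.1-6.6% analytic, 4.9-7.2% simulated. In a more extreme pattern (T1 .2, later .8) it reaches about 7.6-7.7%.
- Single visits under decay in weeks with equal SDs: T4-T1 about 7-10%, T2-T1 about 1.5-3%.
- T4 group difference: about 5% with equal SDs, 6.9% with the unequal SDs.
- At the sizing level of 1.67%: averaged contrast 0.7-6.4%, 3-df test 1.8-3.0%.
- Unstructured covariance on the same simulated data: 4.4-5.6% on every test.

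**The case against.** Four points weigh on the other side.

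First, the text never says random intercept only, and a subject effect can be combined with a residual structure. That is true. A reader might infer that the sponsor has committed to a wrong model, and the documents do not show that. They do name one device and nothing that relaxes it, so the ordinary reading is fair.

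Second, the plan gives the averaged contrast no test level: the interaction is the single test, and the contrast is computed and estimated. This stands. The harm is to the contrast's confidence interval and to any p-value reported with it. Likewise 5% is only a reference level, since the plan analyses at an FDR of 10%.

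Third, the large figures come from assumed patterns. The 8.4-12.9% results need T1 to correlate less with week 8 than weeks 8 and 44 correlate with each other. The AR(1) results ignore the actual spacing. The equal-SD patterns that respect the weeks leave the averaged contrast at 4.8-4.9%; there the 3-df test, at about 5.2% and 5.7%, is slightly further from nominal. This also stands. It rules out saying which way the trial will err, or that the contrast is always the worse affected. The single-visit changes remain off under those same week-based patterns.

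Fourth, cluster-robust standard errors with the random intercept might seem an equal remedy, since they held 4.5-5.7% in the simulation. That simulation used completely random dropout, whereas the plan relies on MAR. In a deliberately extreme check (about 22% dropout driven by the last score, in opposite directions by arm, SD 10, no true effect), the random intercept biased T4-T1 by 0.2-0.46 points and the averaged contrast by 0.04-0.06. Unstructured covariance stayed within 0.04 of zero. The bias is small against the MID of 3.94, but robust standard errors do not remove it.

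**Conclusion.** The point holds as a modest weakness in the analysis specification. On its ordinary reading, the stated device gives wrong error bars for changes from T1 whenever variances or correlations differ by visit, unless the departures happen to cancel. In the patterns tried, the averaged contrast ranges from 2.6% to 12.9% at a nominal 5%, with near-nominal values under equal-SD decay in weeks.

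A reader might go further and conclude that the main test is invalid or that the trial's effect will look more certain than it is. The documents support neither. The interaction test is only mildly liberal, and the direction of error for the contrast is unknown because no visit-pair correlations or visit-specific SDs are given. The conclusion rests on the random-intercept reading, on model-based standard errors, and on the assumed patterns.

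**What to change.** In section 9, Modeling, for normally modelled outcomes, replace the subject random effect with an unstructured within-woman covariance over the four visits, fitted by REML with Kenward-Roger degrees of freedom. Name a fallback for non-convergence: a simpler structure with cluster-robust standard errors by woman. Keep it as a fallback only, for the MAR reason above. State the covariance structure for any outcome given a non-normal distribution.

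The cost is ten covariance parameters instead of two, negligible with about 300 women, plus a few lines of specification and code. No new data are needed. The choice should be fixed before the inferential analyses, which section 10 (Stopping Rules) places after data collection.

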Scheme. Participants will be randomly assigned to group (1:1) using a computer-generated program overseen by [name]. The randomization scheme will be stratified by site (D-H and UAB), time since treatment completion (i.e., <6 months and >6 months), and receipt of chemotherapy (yes versus no) and will be blocked within strata (block lengths of 2 and 4 varied randomly).

Process and blinding. The PI or project managers will manage the randomization process, looking up the id number in an established excel file and assigning the local interventionist to communicate assignment to the participant and initiate treatment activities. The project coordinators will remain blind to group assignment and participants will be instructed not to discuss their assignment with the project coordinator collecting the outcome assessments.

When and How to Withdraw Subjects

Participants will be withdrawn from the study at their request (e.g., lack of interest in or perceived need for intervention, lack of time for study assessments).

Data Collection and Follow-up for Withdrawn Subjects

Our team continues to attempt to contact participants for each session and study assessment unless and until they ask us to stop/express the desire to withdraw. Each study contact is an extension of informed consent where participants are told what is occurring, what happens next, and that their participation is voluntary. When we are unable to reach participants by telephone for at least 30 days we send a letter conveying our attempts to reach them and ask them to contact us to continue with study activities or withdraw, as they prefer.

Treatment Regimen

Theoretical Background of BA/PS

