Data analysis will begin with descriptive statistics for baseline participant characteristics and outcomes by study group. We will calculate means, standard deviations, and percentiles for continuous variables (e.g., participation, quality of life, coping, goal adjustment, distress, age, etc.) and frequencies and proportions for categorical variables (e.g., clinical characteristics), at each time point as appropriate. We will plot and inspect the distributions of the outcome variables, and examine the validity of any extreme values (data entry errors will be minimized by logic checks in the Velos data collection system, and inspection of scheduled reports during data collection). We will examine balance between study groups with respect to baseline characteristics using effect sizes such as the standardized mean difference for numerical variables and Cramer's V for categorical variables. We will examine patterns of missing data due to dropout, and whether baseline characteristics are associated with dropout. Baseline factors showing non-trivial imbalances between groups or that are predictive of dropout, will be then used as adjusting covariates in the longitudinal group comparisons. We will use the latest versions of standard statistical packages (SAS and R) for all analyses.

Group Comparisons (Aim 1, Aim 2, and Exploratory Aim)

Objective. Our objective is to compare the two groups' functional recovery over time in terms of participation (PROMIS scales; Aim 1), productivity (Disability Days and WLQ; Aim 1), quality of life (FACT-B; Aim 2) and coping style, distress, and goal adjustment (Brief COPE, HADS, and GDGRS; Exploratory Aim). All measures are collected at conceptually relevant time points of enrollment (T1), completion of the most intensive part of the intervention (T2), completion of the full intervention (T3) and six months after treatment completion (T4). The methods described below will be conducted upon each outcome variable.

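### Entered only as main effects, the adjusting baseline factors cancel from the planned change-from-T1 effect, so they cannot correct chance imbalance in a factor that predicts change

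*Combined protocol and SAP*

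**What the plan says.** Section 9, Statistical Methods, first sets the rule for choosing covariates: "Baseline factors showing non-trivial imbalances between groups or that are predictive of dropout, will be then used as adjusting covariates" in the longitudinal comparisons. The Modeling paragraph repeats it conditionally: "If necessary, we will conduct covariate adjustment for baseline factors unbalanced between the groups or predictive of dropout".

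The same paragraph fixes the model: a linear mixed model with T1 to T4 as outcomes, time as a categorical variable and a random subject effect. Inference rests on the time by group interaction, the only interaction named. The overall effect is the difference between groups in the mean of T2, T3 and T4 minus T1. LS-means by group and visit are to be reported alongside.

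Handling of Missing Data then relies on the same covariates: "Mixed modeling techniques and covariate adjustment will reduce the impact of missing data". Multiple imputation is added as a robustness check only if dropout exceeds 20%.

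**The concern.** A baseline factor has one value per woman. As a main effect it adds the same amount to her expected score at T1 and at every later visit. The planned effect subtracts T1 from the later visits, so that amount disappears. The rule is meant to protect the comparison against imbalance, but in this form it leaves the treatment effect where it was.

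This matters only for a factor that predicts how much women change. If the factor's effect is the same at every visit, taking change from T1 already removes it.

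Two consequences follow. The result could be presented as covariate-adjusted when the adjustment has not touched the estimate for imbalance. And the missing-data argument is weaker than it reads if dropout depends on a factor that also predicts change.

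**Working it through.** **Inputs from the plan (section 9, Sample Size Determination).** Effect sizes: "the MIDs are 3.94, 3.95 and 11.2 for satisfaction with participation, ability to participate, and quality of life, respectively". SDs: "standard deviation for the two PROMIS scales are both 10 according to the scoring manual and the standard deviation for FACT-B is 24". Test level and visits: "at a corrected significance level of $.05/3=.017$, and with three time-points post baseline". Power and correlation: "to achieve 80% power for within subject correlations ranging from 0.2-0.8". Enrolment is 300, allocated 1:1, with about 20% attrition.

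**Assumed, because the documents give no values.** Size of imbalance, the factor's slope at each visit, the dropout models, and a within-subject correlation of 0.5 (inside the plan's range).

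**Step 1: the plan's own sample size.** n per arm = 2 × [SD × (z(1−α/2) + z(power)) / MID]² × [1 + (m−1)ρ]/m, with m = 3 and two-sided α = 0.017, so the z sum is 2.387 + 0.842 = 3.228 (from unrounded values).
- PROMIS: 2 × (10 × 3.228/3.94)² = 134.3. Times 1.4/3 gives 62.7, so 63; times 2.6/3 gives 116.4, so 117.
- FACT-B: 2 × (24 × 3.228/11.2)² = 95.7. Times 1.4/3 gives 44.7, so 45; times 2.6/3 gives 82.9, so 83.

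All four stated figures are reproduced. The sample size does not depend on the present point.

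**Step 2: the cancellation.** Let D(t) be the raw group difference at visit t, x̄1 − x̄0 the imbalance in factor x, and γ its fitted main effect. With group by time saturated and complete data, the fitted difference at visit t is D(t) − γ(x̄1 − x̄0). The second term is the same at all four visits, so mean[D(2), D(3), D(4)] − D(1) is unchanged. So is each component of the multi-degree-of-freedom interaction test. This holds for any covariance structure. If γ may differ by visit, the contrast moves by −[mean γ(T2–T4) − γ(T1)] × (x̄1 − x̄0), which is the correction wanted.

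**Step 3: fitted check.** One simulated trial, 300 women, complete data, about 0.3 SD imbalance, REML random intercept:

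| Model | Change contrast | SE |
|---|---|---|
| No covariate | −0.41554 | 0.98140 |
| x as main effect | −0.41554 | 0.98140 |
| x by visit | −0.77858 | 0.97683 |

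An unstructured covariance matrix gives the same three estimates. The main effect did move the group difference in T1 LS-means from 1.65 to 0.36.

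**Step 4: size of the imbalance error.** Error = imbalance × (mean slope at T2–T4 minus slope at T1).
- 0.2 SD × 2 points = 0.4; 0.4/3.94 = 10% of the MID.
- 0.3 SD × 2 points = 0.6; 0.6/3.94 = 15%.
- 0.3 SD × 3 points = 0.9; 0.9/3.94 = 23%.

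Simulation with 20% random dropout, 0.3 SD imbalance and no true effect (150 runs, Monte Carlo SE about 0.08) gave mean errors, in the order no covariate / main effect / x by visit, of 0.59 / 0.58 / −0.03 for the 2-point case and 0.89 / 0.89 / −0.01 for the 3-point case.

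**Step 5: against sampling error.** With equal correlations, SE = √{2 × SD² × (1−ρ) × (1 + 1/3)/150}. At ρ = 0.5 this is √(2 × 66.67/150) = 0.94, so 0.4 to 0.9 points is below one SE. At ρ = 0.8 it is √(2 × 26.67/150) = 0.60, and the upper figure exceeds one SE.

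The SE of a standardised imbalance is √(2/150) = 0.115. For any one continuous factor, an imbalance beyond 0.2 SD has probability about 8%. Over nine such factors, taken as independent, the chance of at least one is 1 − 0.917⁹ = 54%.

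**Step 6: factor-dependent dropout.** About 22% missing at T4, no imbalance, dropout depending on x in opposite directions in the two arms (150 runs, Monte Carlo SE about 0.08). Mean error:

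| Slope of x, T1 to later visits | No covariate | Main effect | x by visit |
|---|---|---|---|
| Constant | −0.52 | −0.01 | −0.02 |
| 3 to 5 | −0.62 | −0.15 | 0.14 |
| 0 to 3 | −0.71 | −0.50 | −0.08 |

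A milder model, with dropout depending on x in one arm only (log-odds 1 per SD, 2 to 4 points of change per SD), left −0.13 to −0.23 with the main effect and −0.06 to 0.02 with x by visit. When dropout depended on x in the same way in both arms and x was balanced, no fit showed appreciable error (−0.03 to −0.06).

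**The case against.** The strongest reply is that the plan is silent rather than wrong. It does not restrict covariates to main effects, and naming time by group as the focus of inference is not a full list of model terms. That stands: an analyst could add visit interactions and remain within the text. But main effects are the ordinary meaning of an adjusting covariate, and silence leaves the choice until after the data are seen.

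A reader might infer that the adjustment does nothing at all. The documents do not support that:
- Visit-level LS-means are adjusted.
- Dropout error is essentially removed when the factor's effect is constant over visits.
- With dropout, the cancellation is close but not exact.
- The plan allows other error distributions, including generalized beta; with a non-linear link the cancellation is not exact either.

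A reader might also infer that the trial's estimate is biased. Under randomisation the unadjusted change contrast is unbiased over repeated trials, and its SE already allows for chance imbalance. The errors above are conditional on a given imbalance having occurred.

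The sizes can fairly be called generous. Site, time since treatment and chemotherapy are stratified, so large imbalance in them is unlikely. At ρ = 0.5, 3 points of change per SD implies a correlation of 3/√(66.67 + 9) = 0.34 with averaged change, and the documents support no such value. The dropout error needs dependence that differs between arms. Multiple imputation would cover part of the dropout gap, but only above 20% dropout and only as a robustness check.

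**Conclusion.** The point holds in a limited form. With covariates read as main effects, a linear model and complete data, the planned adjustment leaves the group by time test and the change contrast exactly as they were. With about 20% random dropout it leaves them nearly so. It therefore cannot correct chance imbalance in a factor that predicts change, which is the only kind of imbalance that needs correcting for this effect. For factor-dependent dropout it is sufficient when the factor's effect is constant and partial when the factor also predicts change.

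The cancellation is algebra. The sizes rest on assumptions: about 0.4 to 0.9 points (10 to 23% of the MID) for imbalance of 0.2 to 0.3 SD and 2 to 3 points of change per SD, less than one SE at a correlation of 0.5. The residual dropout error is about 0.1 to 0.5 points, depending on the dropout model.

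The documents do not show that visit interactions are ruled out, nor that the final estimate will be wrong. They do show a stated remedy that, read in the usual way, misses its main target. LS-means that look balanced beside an unadjusted effect could hide this. It should be corrected; it does not threaten the design or the sample size.

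**What to change.** In section 9, state in both Statistical Methods and Modeling that every adjusting baseline factor enters together with its interaction with visit. Repeat this where Handling of Missing Data relies on covariate adjustment.

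Alternatively, model T2 to T4 only as responses, with the T1 score (by visit) and the factors as covariates. Main effects then do adjust the group differences. The primary test would need restating as the group differences at T2 to T4, because a group by visit term across those three visits alone no longer captures the overall effect.

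The first option costs a sentence or two and 3 extra degrees of freedom per numerical factor, or 3 × (k − 1) for a factor with k categories, out of about 300 women. The list of adjusting factors should stay short for that reason. Section 10 defers inferential analysis until data collection is complete, so the wording can be settled beforehand. No change to data collection or sample size is needed.
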